Rash	
Some observations of rash with oral RPV have been reported in clinical studies executed to date (the majority are mild).
 
Severe skin and hypersensitivity reactions have been reported during the post-marketing experience with oral RPV-containing regimens, including cases of Drug Reaction with Eosinophilia and Systemic Symptoms (DRESS). While some skin reactions were accompanied by constitutional symptoms such as fever, other skin reactions were associated with organ dysfunctions, including elevations in hepatic serum biochemistries.
	
 
Participants with a Grade 1 or 2 rash will be allowed to continue treatment or to be rechallenged, depending on the clinical judgment of the investigator.
 
All participants developing a Grade 3 or 4 rash should discontinue study drugs and be withdrawn from the study.
 
All rash events should be assessed with special attention to systemic symptoms, laboratory abnormalities, or mucosal involvement. Close clinical follow-up, including follow-up of laboratory abnormalities, and appropriate medical intervention, including referral to dermatologist as appropriate, should be instituted for these events; daily follow-up is recommended for 5 days from the onset of the event to monitor for progression of the event. In case of cutaneous reaction/rash and/or an allergic reaction, the use of cetirizine, levocetirizine, loratadine, diphenhydramine, topical corticosteroids, or antipruritic agents is permitted.
 

Potential Risk of Clinical Significance	Summary of Data/Rationale for Risk	Mitigation Strategy

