Inadvertent Intravenous Injection (Accidental Maladministration)	
As with any intramuscular injection, it is possible that CAB LA and/or RPV LA can be inadvertently administered intravenously instead of intramuscularly possibly resulting in higher than expected concentrations of CAB and/or RPV shortly after injection and lower concentrations thereafter. This could be due to administrator error, improper injection technique and / or improper needle length used based on body type.
	
 
Training will be provided to all sites on proper injection technique.
 
Should IM maladministration be suspected at any time (e.g., suspected under or overdose or inadvertent intravenous [IV] dosing), post dose ECG monitoring and vital signs or any other supportive testing may be obtained at the discretion of the investigator, and the medical monitor notified.
 
2-hour post dose PK samples will be for determination of CAB and RPV concentration and possible pharmacokinetic correlation with safety parameters such as ECG changes.
 

Hypersensitivity Reactions (HSR)	
Hypersensitivity reactions have been reported as uncommon occurrences with integrase inhibitors (INI), including the closely related compound dolutegravir, and were characterized by rash, constitutional findings, and sometimes, organ dysfunction, including liver injury.
 
While there have been no clinical cases of hypersensitivity to CAB to date, there is a theoretical risk of systemic or severe hypersensitivity reactions with or without hepatic symptoms associated with use of IM CAB. The long exposures anticipated after IM CAB injection may complicate the management of a drug hypersensitivity reaction, were it to occur.
	
 
The risk of developing a hypersensitivity reaction post administration of CAB and RPV will be minimized by the use of a 4-week oral lead-in of oral CAB/RPV to determine individual safety and tolerability prior to the introduction of IM CAB.
 
Clinical assessments, laboratory tests (including liver transaminases) and vital signs will be performed throughout this study. Results from these assessments may aid early detection of HSR.
 
Oral CAB will be withdrawn immediately for cases with suspected HSR during the oral CAB/RPV lead-in phase and participants would not proceed to the injection phase. Any HSR reactions that occur would be managed supportively.
 

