## **4.2. Justification for Dose**

### **4.2.1. Oral Dose:**

The risk of developing a hypersensitivity reaction (HSR), post administration of CAB LA and RPV LA is minimized by the use of a 4-week OLI of oral CAB and RPV. In the event of a suspected HSR, participants will not receive CAB LA and RPV LA injections. The management of participants with HSRs following receipt of drugs with a long half-life may be challenging. HSRs have been reported as uncommon occurrences with integrase CAB and RPV, and were characterized by rash, constitutional findings, and sometimes, organ dysfunction, including liver injury. The time of onset of HSR reactions supports the proposed duration of the OLI with the majority of HSRs occurring within the first 28 days of exposure to the drugs.

During the OLI phase of this study, oral formulations of CAB + RPV will be co-administered to assess safety and tolerability in each participant prior to IM dosing with CAB LA and RPV LA. The combination of oral RPV 25 mg QD and CAB 10, 30, and 60 mg QD has been used as OLI in HIV-1 infected participants in both Phase IIb studies, the pivotal Phase 3 studies (FLAIR and ATLAS), and Phase 3b study ATLAS-2M.

In these studies, all three oral CAB doses demonstrated similar efficacy at the Week 48 primary endpoint. However, 30 mg dose was selected as OLI for all CAB LA studies, as it delivered higher steady-state exposures than predicted for the monthly or every 2-month regimen. CAB 30 mg is also the OLI treatment intended for marketing. Therefore, CAB 30 mg along with marketed dose of RPV 25 mg (EDURANT) will be used as the OLI dosing in this study and will achieve exposures sufficiently high to assess safety and tolerability during a short OLI prior to a single IM injection of CAB LA + RPV LA formulations.

The PK collected during the OLI phase will be utilized along with the data from LA injection phase to precisely estimate PK parameters using a robust population PK (PoPPK) model. A window of 10 to 14 days (covering ~7-10 half-lives) will be used for wash-out period prior to LA injection accounting for variability in half-life in participants. This wash-out period would prevent plasma concentrations after oral administration from being mixed with plasma concentrations on Day 1 after LA IM injection.

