# **7. DISCONTINUATION OF STUDY INTERVENTION AND PARTICIPANT DISCONTINUATION/WITHDRAWAL**

## **7.1. Discontinuation of Study Intervention**

Participants may voluntarily withdraw from the study at any time and for any reason. Site investigators and study staff may withdraw participants before their scheduled termination visit for safety, behavioral, or administrative reasons, or if the participants are unable or unwilling to comply with study procedures. The reasons for withdrawals will be recorded in the participants' study records. If a participant withdraws from the study, he/she may request destruction of any samples taken, and the investigator must document this in the site study records.

During the oral lead-in period, early withdrawal on medical grounds will occur if the participant develops a Grade 3 or higher AE that is judged by the investigator to be related directly to the study product (see [Appendix 3](#) and [Appendix 4](#) for definitions and grading of severity of adverse events), or a participant develops a grade 3 or higher clinical significant laboratory abnormality (see Division of AIDS [DAIDS] table [Appendix 7](#) for grading) or any AE that is deemed clinically significant by the investigator and is judged by the investigator to be related directly to the study product.

For liver-related stopping criteria, please refer to Section [7.1.1](#).

If a participant receives the injections, they will be followed 52-weeks post the final injection per protocol for appropriate procedures, including blood plasma PK sampling, and safety evaluations, and will not be removed from the study for medical reasons, unless they refuse to continue participation.

[figure not shown]
During the oral lead in phase additional pre-specified reasons for discontinuing a participant from the study (or, at minimum, discontinuing administration of study product and continuing safety evaluations) include:

- Pregnancy (please see Section 8.2.5)
- Protocol deviation
- Non-compliance
- Participant withdraws consent
- Participant lost to follow-up
- Investigator discretion
- Sponsor discontinues study

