### Assessment of Causality

- The investigator is obligated to assess the relationship between study intervention and each occurrence of each AE/SAE.
- A "reasonable possibility" of a relationship conveys that there are facts, evidence, and/or arguments to suggest a causal relationship, rather than a relationship cannot be ruled out.
- The investigator will use clinical judgment to determine the relationship.
- Alternative causes, such as underlying disease(s), concomitant therapy, and other risk factors, as well as the temporal relationship of the event to study intervention administration will be considered and investigated.
- The investigator will also consult the Investigator's Brochure (IB) and/or Product Information, for marketed products, in his/her assessment.
- For each AE/SAE, the investigator **must** document in the medical notes that he/she has reviewed the AE/SAE and has provided an assessment of causality.
- There may be situations in which an SAE has occurred, and the investigator has minimal information to include in the initial report to GSK. However, **it is very**

**important that the investigator always make an assessment of causality for every event before the initial transmission of the SAE data to GSK.**

- The investigator may change his/her opinion of causality in light of follow-up information and send an SAE follow-up report with the updated causality assessment.
- The causality assessment is one of the criteria used when determining regulatory reporting requirements.

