#### **Female Participants who become pregnant**

- Investigator will collect pregnancy information on any female participant, who becomes pregnant while participating in this study.
- The initial information will be recorded on the appropriate form and submitted to GSK within 24 hours of learning of a participant's pregnancy.
- Participant will be followed to determine the outcome of the pregnancy. The investigator will collect follow up information on participant and neonate, which will be forwarded to GSK. Generally, follow-up will not be required for longer than 6 to 8 weeks beyond the estimated delivery date.
- Any termination of pregnancy will be reported, regardless of fetal status (presence or absence of anomalies) or indication for procedure.
- While pregnancy itself is not considered to be an AE or SAE, any pregnancy complication or elective termination of a pregnancy for medical reasons will be reported as an AE or SAE.
- A spontaneous abortion (occurring at < 22 weeks gestational age) or still birth (occurring at > 22 weeks gestational age) is always considered to be an SAE and will be reported as such.
- Any SAE occurring as a result of a post-study pregnancy which is considered reasonably related to the study intervention by the investigator, will be reported to GSK as described in [Appendix 3](#). While the investigator is not obligated to actively seek this information in former study participants, he or she may learn of an SAE through spontaneous reporting.

Any female participant who becomes pregnant in OLI phase. will discontinue study intervention if participant gets pregnant and will not receive IM injections.  
If participant gets pregnant after receiving CAB LA and RPV LA, the participant should be followed up through 52 weeks post injections.

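### On suspected hypersensitivity in the oral lead-in, the protocol orders only oral CAB stopped; the rule should name oral RPV as well.

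*Protocol*

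**What the plan says.** The Hypersensitivity Reactions row of Protocol Section 2.3.1 sets the action for a suspected HSR before injection: "Oral CAB will be withdrawn immediately for cases with suspected HSR during the oral CAB/RPV lead-in phase". It adds that such a participant does not go on to injection. The row mentions RPV when it describes the lead-in and the risk, but not as a drug to be stopped.

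On the evidence for each drug, the same row begins a sentence with "While there have been no clinical cases of hypersensitivity to CAB to date" and goes on to call the risk theoretical. The Rash row states: "Severe skin and hypersensitivity reactions have been reported during the post-marketing experience with oral RPV-containing regimens", and includes DRESS among the cases. Section 4.2.1 (Oral Dose) says that HSRs have been reported, uncommonly, with CAB and RPV. It then gives its own consequence: "In the event of a suspected HSR, participants will not receive CAB LA and RPV LA injections". It does not mention the tablets.

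The general rule is in Section 7.1. During the lead-in, withdrawal on medical grounds follows a related adverse event of Grade 3 or higher, a clinically significant laboratory abnormality of Grade 3 or higher, or "any AE that is deemed clinically significant by the investigator and is judged by the investigator to be related directly to the study product".

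**The concern.** The two drugs are taken together, so at the moment of suspicion neither can be cleared as the cause. The immediate stop nevertheless covers only one of them, and the one left out is a drug that the protocol itself associates with severe hypersensitivity. No passage gives a reason for stopping CAB alone.

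A literal reading could be acted on. The two drugs are separate tablets in separate bottles (Sections 6.1.1.1 and 6.1.1.2), and participants dose mostly at home after Day 2, with the next scheduled visit on Day 14 (Section 4.1.2). A site that repeated the row word for word to a participant would stop one bottle. Further oral RPV would serve no study purpose, because both injections are already barred. What is at stake is participant safety.

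**Working it through.** No arithmetic applies. The check sets the stopping provisions side by side and asks which of them reach oral RPV.

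| Provision | Trigger | What stops |
|---|---|---|
| 2.3.1, HSR row | Suspected HSR in lead-in | Oral CAB; no injections |
| 4.2.1 | Suspected HSR | Both injections; silent on tablets |
| 2.3.1, Rash row | Grade 3 or 4 rash | Both drugs; participant withdrawn |
| 2.3.1, Rash row | Grade 1 or 2 rash | Nothing required; continuing or rechallenge allowed |
| 7.1.1 and Appendix 6 | ALT at least 3 times ULN | All study intervention |
| 7.1, medical grounds | Grade 3 or higher related AE, or any clinically significant and directly related AE | Participant withdrawn |
| 7.2 | Withdrawal from study | All study intervention, permanently |
| 8 | Any safety concern | Nothing automatic; immediate sponsor discussion on whether to continue |
| Appendix 4 | Pregnancy in lead-in | All study intervention; no injections |

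**Step 1: rules triggered by suspicion.** Only the first two rows act on suspected HSR. One stops oral CAB and the other concerns injections. Neither orders oral RPV stopped.

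**Step 2: rules that reach RPV by another route.** Section 6 includes oral RPV in the investigational product, so the general terms used in Sections 7.1 and 7.2 cover it. A suspected HSR that shows as severe rash or marked ALT elevation, or that is judged clinically significant and directly related, therefore ends RPV too.

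**Step 3: what remains.** The open case is a suspected HSR below Grade 3, with ALT under 3 times ULN, that the investigator has not yet judged both clinically significant and directly related. The causality standard in Appendix 3 asks for "facts, evidence, and/or arguments to suggest a causal relationship, rather than a relationship cannot be ruled out". Suspicion can come earlier than that. In that interval the HSR row stops CAB, and RPV is left to judgment and to the sponsor discussion.

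**Step 4: likely intent.** Three places suggest that both drugs were meant.
- The pre-injection withdrawal visit is timed from the last oral dose of both drugs (Section 1.3.1, footnote 9; Section 4.1.4).
- The lead-in pregnancy rule uses the collective term: the participant "will discontinue study intervention if participant gets pregnant and will not receive IM injections".
- Appendix 8 shows a similar slip. It refers to 28 days of oral CAB dosing, where footnote 5 of Section 1.3.1 refers to CAB and RPV.

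**Step 5: effect on the analysis.** The primary PK endpoints come from the injection phase (SAP Section 8.2). A participant with suspected HSR has no injection under either wording, so the primary analysis is the same.

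**The case against.** The strongest reply is that the risk table is a summary and that Section 7 governs discontinuation. A participant barred from injection is in effect being withdrawn, and withdrawal ends all study intervention. To suspect a drug reaction during dosing is already close to a causal judgment, and Appendix 3 lists timing among the things to weigh. For RPV to continue alone, the investigator would have to suspect HSR strongly enough to stop CAB, yet not find the event significant and related, and no RPV stop could follow from the sponsor discussion. Most of this stands, and it is why the point is minor. It does not remove the error. The row written for this event acts at once on suspicion and names one drug, Section 7.2 applies only after a decision to discontinue, and Section 8 requires a discussion, not a stop.

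A reader might infer three stronger things that the documents do not support:
- **That the plan intends RPV to continue alone through the rest of the lead-in.** The withdrawal timing and the general rules point the other way.
- **That the absence of HSR from the bulleted list in Section 7.1 shows it was overlooked.** That list is introduced by "During the oral lead in phase additional pre-specified reasons for discontinuing a participant from the study" and follows the medical-grounds paragraph, where an HSR would fall as an adverse event. Severe rash, liver and QTc stops are not in the list either, and each has its own rule.
- **That RPV is the likelier culprit.** The Rash row speaks of regimens containing RPV, and Section 4.2.1 names both drugs, which sits awkwardly with the HSR row's statement on CAB. The documents support stopping both, but not ranking them.

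**Conclusion.** The HSR stopping sentence is incomplete as written: it should cover both co-administered oral drugs and covers one. This is a low-severity safety-wording error, probably a drafting slip, with no effect on the PK analysis. The general rules would nearly always stop RPV as well, so the practical gap is confined to the short interval between suspicion and a judgment of significance and relatedness, in cases without severe rash or the ALT threshold. The conclusion rests on the public text. Site instructions in the Study Reference Manual are not available and may already say to stop both. The documents give no HSR rate, so no expected number of participants or doses is claimed.

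**What to change.** In the HSR row of Section 2.3.1, change the start of the sentence to *Oral CAB and oral RPV will both be withdrawn immediately* and leave the rest as it is. Optionally, add a reference to suspected HSR in the lead-in medical-grounds paragraph of Section 7.1, so that the discontinuation section and the risk table agree.

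No permanent bar on restarting is proposed. It would go beyond the question of which drugs stop, and it would conflict with the Rash row's allowance for rechallenge after a Grade 1 or 2 rash. That allowance can stay.

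The cost is a wording amendment, which needs IRB/IEC approval under Section 11.1.1. It adds no visit, sample, procedure or participant, and the SAP does not change.

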### **2.3.1.1. Other Clinically Relevant Information**

Additional details concerning safety observations from clinical studies and for which a causal association has not been established or which are of minimal clinical significance may be found in the Investigator's Brochures. Refer to 'Summary of data and guidance for the investigator'.

#### **Seizure**

Several cases of seizure have occurred during the CAB program. These cases have had alternative explanations for their occurrence. Overall, there is not convincing evidence that CAB exposure may be causally associated with seizure or with reduction of seizure threshold, due to the low frequency of reports, the confounders present in the cases received to date and lack of any pre-clinical signal or identified plausible mechanism. However, seizure and seizure-like events are considered as AEs of special interest for CAB. Participants with an unstable or poorly controlled seizure disorder will be excluded from study participation. Report any cases of seizure or seizure like events within 24 hours of the event.

### **2.3.2. Benefit Assessment**

Participants participating in this study will not receive any clinical benefit but will be compensated for their time and participation.

Benefit considerations may include satisfaction from knowledge that participants have contributed to the process of developing new therapies for HIV.

### **2.3.3. Overall Benefit: Risk Conclusion**

Review of the cumulative safety data on CAB and RPV have not identified any safety signals which are considered to pose an unacceptable risk to healthy participants.

Considering the multiple and overlapping measures that will be taken to minimize risk to participants participating in this study, the potential risks identified in association with CAB and RPV are justified by the anticipated benefits that may be afforded to participants including the satisfaction of contributing to the ongoing continued clinical development of CAB and RPV for both the treatment and prevention of HIV infection.

### 3. OBJECTIVES AND ENDPOINTS

Objectives	Endpoints
Primary	

 
To describe the PK profiles of CAB and RPV following a single intramuscular injection each of CAB LA + RPV LA administered to the lateral thigh muscle in adult healthy participants
 
	
 
Maximum observed concentration (Cmax) and time of maximum observed concentration (tmax) in plasma
 
Area under the concentration – time curve from time zero to last quantifiable time point (AUC(0-t)) through the follow-up phase
 
Area under the concentration – time curve from time zero to infinity (AUC<math>0-\infty</math>)
 
Apparent terminal phase half-life (t<math>1/2</math>) and absorption rate constant (KALA))
 

Safety	

 
To assess safety and tolerability of CAB and RPV following repeated oral dose and single intramuscular injection in the lateral thigh of adult healthy participants
 
	
 
Safety and tolerability parameters including adverse events, clinical laboratory tests, ECG, and vital sign assessments
 

Objectives	Endpoints
Exploratory  CCI	

## 4. STUDY DESIGN

### 4.1. Overall Design

This is a phase 1, open label study in healthy participants to assess the PK of CAB and RPV in plasma following a single 600 mg (1 x 3 mL) and a 900 mg (1 x 3 mL) injection each; respectively, administered IM to separate *vastus lateralis* muscles on each leg.

The study will consist of

- 30-day screening period
- 28-day oral lead-in (OLI) phase at a CAB dose of 30 mg and RPV dose of 25 mg once a day with a meal
- 10 – 14 days washout period
- CAB and RPV injection, administered IM: 600 mg (1 x 3 mL) CAB on left and a 900 mg (1 x 3 mL) RPV injection on right *vastus lateralis* muscle
- Sparse PK sampling for up to 29 days in OLI and serial PK sampling for up to 4 weeks after the injection, per SoA. Participants will return for safety assessments and additional PK sampling at Week 8, 12, 24, 36, and 52 post last injection during the follow-up phase.

Approximately 15 adult healthy participants will be dosed with injectable study interventions. If participants prematurely discontinue the study, for any other reason, other than an AE, additional replacement participants may be enrolled at the discretion of the Sponsor in consultation with the investigator.

Approximately 30% of female participants will be enrolled.

